2.2. Scientific Rationale

The test product formulation is based on the most promising clinical research on natural ingredients to safely impact the immune system and reduce duration of the common cold. While the evidence to support the use of these individual active ingredients is growing, well-designed human clinical trials showing benefit are necessary to demonstrate efficacy of the test product's unique formulation.

The present study will include at least 200 adult participants in the general population who are seeking herbal remedies to reduce the duration of their common cold symptoms.

2.2.1.Potential Risk

Minimal risk is foreseen for participants through their participation in the study. All the ingredients composing the test product are Generally Recognized as Safe (GRAS) by the FDA for daily consumption at their present concentrations.

The ingredients in the test product have shown to have some theoretical drug interactions which have been listed in the appendix.

Potential side-effects have been observed in high doses which are significantly greater than the dose of the capsule as recommended in the instruction for use:

- · epigastric pain
- nausea
- vomiting
- loss of appetite
- abdominal cramps
- diarrhea
- headaches

This study is determined by Sponsor and Principal Investigator to be a Minimal Risk Study.

Minimal risk is defined by 45 U.S. Code of Federal Regulations (CFR) 46.102 (i) as follows:

"Minimal risk means that the probability and magnitude of harm or discomfort anticipated in the research are not greater in and of themselves than those ordinarily encountered in daily life or during the performance of routine physical or psychological examinations or tests."

Refer to: http://www.hhs.gov/ohrp/humansubjects/guidance/45cfr46.htm#46.102

2.2.2. Known Potential Benefits

Over-the-counter and prescription remedies aimed toward relieving the symptoms of the common cold may have known undesirable side effects Study participants may benefit from the test product by eliminating unwanted exposure to undesirable ingredients and side effects of other-the-counter drugs when treating a common cold, while still achieving symptom relief and reducing the duration of their cold.

2.2.3. Minimization of Risks

Research participants will be carefully screened to meet enrollment criteria. Participants meeting exclusion criteria will not be enrolled. The study participant informed consent will be presented with clear description of the study requirements and opportunity to have questions answered before enrollment will be provided. Once an event occurs, review of symptoms will be

ascertained daily until symptoms have resolved or for 18 days. Reporting of adverse events will be reviewed routinely and in accordance with regulatory guidelines (21CFR, GCP) by the Principal Investigator. Participants with occurrence of worsening symptoms or adverse events will be advised to stop the product and may seek medical attention and exit the study.

3. Study Objectives

The purpose of the present study is to evaluate 1) the impact of the Immune Support test product on the duration of symptoms of the common cold in adult participants and 2) the subjective experience of these participants related to general health, common cold symptoms, and personal experience with the product. [13, 18, 29, 32]

This will be evaluated based on the primary and secondary endpoints. These endpoints, the analysis populations, and their respective measures are described below. Further details on the methods for measuring the outcomes can be found in the Study Outcome Measures and Analysis Plan sections.

Primary Endpoint:

The primary endpoint will be time to freedom from cold symptoms, with the clock starting at the onset of the cold. Where the onset is defined as the point in time when the participant experiences 2 or more cold symptoms. The primary analysis will be a Kaplan-Meier analysis of time to absence of all symptoms, based on the participants' self-report. There is no control group for the primary analysis. [5]

Secondary Endpoint:

- Secondary endpoints involve the duration and severity of the separate cold symptoms.
- Comparison against the participant's normal behavior.
- Net Promoter Score.
- Adverse events will be summarized.
- An additional data presentation will consist of results from both Treatment and Control in similar studies appearing in the literature. There will be no formal statistical comparison of results from this study and historical studies.

4.Study Design

The present study will be a single site, prospective, single arm observational study of minimal risk consisting of at least 200 participants who suffer from cold symptoms. The participants must meet additional inclusion/exclusion criteria (see Inclusion/Exclusion Criteria). Participants will begin taking the powder drink-mix at the onset of their cold symptoms. Onset is defined as the point in time the participant experiences 2 or more cold symptoms (cough, hoarseness, muscle ache, nasal drainage,

nasal congestion, scratchy throat, sore throat, sneezing, or an oral temperature greater than 37.7 °C (99.9 °F)). When the participant experiences 2 or more symptoms, they will report symptoms in the cold start form. If they meet the criteria for a cold, they will start completing the daily cold symptom diary prior to taking the test product. After consuming the product, the participant will complete the cold symptom diary daily until all symptoms resolve. Since none of the ingredients in the test product have been seen to provide relief from fever or pain, the participant will be allowed to take a pain reliever and fever reducer (e.g. ibuprofen or acetaminophen). If medication is taken, the participant will record this in their symptom diary.

Study enrollment and management will be decentralized, where participants do not visit an investigator or a clinic for clinical assessment. The participants will participate in the study at home. All data collected from during this study will be reported by the participant via eCRFs, eDiary, and other electronic data entries. If a visit is required, it will be conducted via remote contact by telephone.

4.1.Test Product

Overview:

Participants in this study will consume the test product twice a day (4-6 hours apart) at the onset of cold symptoms. The participant will mix one packet of the test product in 6-8 ounces of water. The test product will be delivered to the participants' residence in a single shipment consisting of an18-day supply (36 packets) of the test product. The study participant will mix the contents of the packet into 6-8 oz. of hot water and drink twice a day during the duration of the cold.

Below is the description of the test product and its ingredients.

Test Product

Description: Combining whole food sourced Vitamin C, Echinacea, Ivy Extract, Zinc, Ginger and Turmeric. This formula is designed to support the immune system while reducing the duration of cold.

Active Ingredients: Echinacea, Ivy Extract, Camu (Vitamin C), Ginger, Turmeric, Zinc.

Inactive Ingredients: Natural Flavor, Guar Gum, Monk Fruit Sweetener, Citric Acid.

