- Participant will take the test product twice a day, at least 4-6 hours apart.
- The next day the participant will complete their symptom diary prior to taking the test product. Once completed they will mix 1 packet of the test product into 6-8 oz of water and consume the whole drink. They will take the test product again 4-6 hours later.
- The participant will complete this process daily until their cold symptoms resolve or for 18 days, whichever is shorter.
- If the participant takes ibuprofen or acetaminophen at any time, the participant will record this on their symptom diary.
- After taking the test product, the participant will be instructed to fill out an Adverse Event form for any side-effects experienced.
- The participant will be prompted, by email, to complete the study exit form once the participant's symptoms resolve completely or after 18 days, whichever is shorter.
- Neither the sponsor nor Hawthorne Effect, Inc. will make any attempt to collect any unused test product.
- Upon receipt of study exit survey and review of completed study forms, participant will receive an Amazon gift card of \$25 via email.

6.2.Study Schedule of Activities

Assessments	Screening	Consent	Before Receipt of Test Product	Product Received	Event Start Date**	Days 1-18*	Study Exit***
Study Window							
Screening Survey	Х						
Consent		Х					
Baseline Survey			х				
Demographics			х				
Acknowledgement of Receipt of Test Product				Х			
Test Product Consumed****					Х	Х	
Symptom Diary					Х	Х	Х
Meds & Supplements			Х				
AE Assessment					Х	Х	Х
Study Exit Survey							Х

^{*}Participant will participate in the study starting on the day of the cold until the cold symptoms resolve or 18 days whichever is shorter.

^{**} The day the participant experiences 2 or more of the protocol defined symptoms

^{***} The participant will exit the study at the time of complete cold symptom resolution, 18 days after the start of cold symptoms, or at 90 days if no cold is experienced by the participant.

^{****} The product will be consumed twice a day, 4-6 hours apart

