6.4. Adverse Event and Safety Monitoring

Adverse Events (AEs) are defined as any untoward medical occurrences described by the study participant. All AEs will be self-reported and documented on the platform. The AEs will be reviewed by the study team including the remote trial coordinator and study principal investigator and reported according to the IRB requirements. Participants who experience adverse events will be advised to stop taking the test product and seek medical attention.

In the event that a participant experiences an adverse event, the clinical study manager or clinical ops coordinator will notify both the PI and Sponsor. The Sponsor will take appropriate action according to their standard operating procedures for any adverse events that warrant action by the sponsor.

6.4.1.Anticipated Adverse Events

Anticipated Adverse Events are complications that are known to be associated with the test product (in high doses exceeding recommended use):

- epigastric pain
- nausea
- vomiting
- loss of appetite
- abdominal cramps
- diarrhea
- headaches

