13.1.2. Appendix B Instructions for Use

Instructions for Use

The test product combines whole food sourced Vitamin C, quality Echinacea, Ivy Extract, Zinc, Ginger and Turmeric. This formula is designed to support the immune system while soothing & clearing cough, with the main active components of Echinacea fresh pressed juice, Ivy Extract and Zinc

Daily Dosage:

1 Packet contain: Active Ingredients: Echinacea, Ivy Extract, Camu Camu, Ginger, Turmeric, Zinc

Inactive Ingredients: Natural Flavor, Guar Gum, Monk Fruit Sweetener, Citric Acid

Serving Size 1 Sachet (5.4g)		
Servings per Container 3		
	Amount Per Serving	% Daily Value
Calories	5	
Total Carbohydrate	1 g	<1%
Total Sugars	<1 g	†
Vitamin C (as Camu-camu (Fruit) Powder & Ascorbic Acid)	500 mg	833%
Zinc (as Zinc Gluconate)	15 mg	100%
Organic Turmeric Powder (Rhizome)	500 mg	†
Echinacea purpurea Extract (Aerial)	400 mg	†
Organic Ginger Powder (Root)	250 mg	†
English Ivy Extract (Leaf)	25 mg	†

OTHER INGREDIENTS: Natural Flavor, Guar Gum, Monk Fruit Extract, Citric Acid

Directions: Mix 1 packet with 6-8 oz of hot water at the onset of symptoms and repeat twice a day, 4-6 hours apart, for the duration of your cold symptoms.

*These statements have not been evaluated by the Food and Drug Administration. This product is not intended to diagnose, treat, cure or prevent any disease.

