13.1.5. Appendix E Symptom Diary

Daily Symptom Survey

BEFOREtaking the test product OR any allowed medication, please answer all of the following questions daily for the duration of your cold symptoms.

REMINDER: DURING THE TRIAL, YOU ARE NOT ALLOWED TO TAKE ANY COLD MEDICATIONS (NYQUIL/DAYQUIL, TYLENOL COLD, COUGH SYRUP/LOZENGES, ETC.)

1. Cough			
0	1	2	3
No Symptom	Slight	Moderate	Severe
2. Hoarseness			
0	1	2	3
No Symptom	Slight	Moderate	Severe
3. Muscle aches			
0	1	2	3
No Symptom	Slight	Moderate	Severe
4. Runny Nose			
0	1	2	3
No Symptom	Slight	Moderate	Severe
5. Nasal Congestion			
0	1	2	3
No Symptom	Slight	Moderate	Severe
6. Scratchy Throat			
0	1	2	3
No Symptom	Slight	Moderate	Severe

7. Sore throat

0	1	2	3
No Symptom	Slight	Moderate	Severe
8. Sneezing			
0	1	2	3
No Symptom	Slight	Moderate	Severe

- 9. Did you take any pain/fever reducer (ibuprofen/acetaminophen today? (Y/N)
 - a. Why?
 - b. Did it work? (Y/N)
- 10. Have you taken any other cold medications (Nyquil, Dayquil, other cold medication, cough drop, cough syrup, etc.)? (Y/N)
 - a. If yes, please exit from the study
- 11. Have you seen a doctor for your symptoms? (Y/N)
 - a. If yes, were you prescribed anything? $(Y/N) \rightarrow$ if yes please exit from the study
- 12. Did you experience any side effects after taking the product? (Y/N)
 - a. If yes, please fill out the Adverse Event form.

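### The protocol promises stop-product advice after an adverse event, but none of the three available participant forms on dosing or side effects prints it, and the written steps lead from the diary to the next packet

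*Combined protocol and SAP*

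**What the plan says.** The commitment appears twice in the protocol body. Under Minimization of Risks (2.2.3), participants with "worsening symptoms or adverse events will be advised to stop the product and may seek medical attention and exit the study". Under Adverse Event and Safety Monitoring (6.4): "Participants who experience adverse events will be advised to stop taking the test product and seek medical attention".

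On staff action, 2.2.3 says "Reporting of adverse events will be reviewed routinely", and adds that this follows regulatory guidelines. Section 6.4 says "The AEs will be reviewed by the study team including the remote trial coordinator and study principal investigator", with reporting under IRB requirements and notification of the principal investigator and sponsor. Neither section says who advises the participant, by what channel or how soon.

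The participant's own steps are in Study Procedures (6.1) and the appendices:

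- **6.1, daily sequence.** The diary comes before the product. Then: "Once completed they will mix 1 packet of the test product into 6-8 oz of water and consume the whole drink". A second packet follows 4-6 hours later.
- **6.1, side effects.** After taking the product, "the participant will be instructed to fill out an Adverse Event form for any side-effects experienced".
- **Instructions for Use (Appendix B).** The participant is to "repeat twice a day, 4-6 hours apart, for the duration of your cold symptoms".
- **Symptom diary item 12 (Appendix E).** After a yes to side effects: "If yes, please fill out the Adverse Event form".
- **AE form (Appendix G).** It lists ten named symptom groups plus an open category. It then asks for a description, the timing, what was done about it, any medical care received, and hospital paperwork.

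**The concern.** The stop advice is one of the protocol's stated risk controls. The study is remote and self-dosed: there are no clinic visits, and the full supply of 36 packets is sent to the home in one shipment. In this setting the paper or screen in front of the participant acts first, and staff act only after a report reaches them. Section 6.1 also provides paper copies for people who cannot log in, and a report made that way may reach staff later.

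The forms are silent at the moment when the decision to dose is made. A participant who answers yes to item 12, completes the AE form and follows the written order then mixes the next packet. The AE form itself names possible serious reactions, among them throat swelling, wheezing, chest pain and one-sided weakness, without telling the reader to stop or to get help. What is at stake is avoidable further exposure after a reaction. It is a safety matter rather than a threat to the primary estimate.

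**Working it through.** The plan gives no figure to reproduce here. The check is a comparison of texts followed by a small count.

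**Step 1. Where the advice is printed.** It is in 2 of 2 protocol sections on handling adverse events (2.2.3 and 6.4). It is in 0 of 3 available participant forms on dosing or side effects (Instructions for Use, diary, AE form). The side-effect bullet in 6.1 does not carry it either.

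**Step 2. Whether the diary can carry an instruction.** Of its four yes/no items (9 to 12), items 10 and 11 tell the participant to leave the study, after another cold remedy or a prescription respectively. Item 12 points only to the AE form. So a printed direction fits the existing format. The comparison goes no further, because items 10 and 11 enforce the participation rules in 4.2 and are not safety advice.

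**Step 3. How many further packets.** Inputs: 2 packets per day (4.1, 6.1), and a delay of d days from report to staff contact. The plan does not state d, so the values below are assumptions. A participant who keeps following the forms until contacted takes 2 × d packets over d whole days.

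| Report route and assumed contact | Further packets |
|---|---|
| AE form filed after a dose; contact before the next packet is due | 0 |
| Pre-dose diary report; contact that day, before the second packet | 1 |
| Contact after d = 1 day | 2 × 1 = 2 |
| Contact after d = 2 days | 2 × 2 = 4 |
| Contact after d = 3 days | 2 × 3 = 6 |

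The range is 0 to 6 for contact within 3 days. The floor is 0 because 6.1 lets the AE form be filed straight after the dose that caused the reaction. The supply does not set a practical limit: 2 × 18 = 36 packets, so 36 − 2 = 34 remain at the day-2 diary. That figure describes stock in the home, not risk.

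**Step 4. How narrow an urgent-care prompt can be.** The reactions that plainly call for immediate care are throat, lip or tongue swelling; wheezing; chest pain; fainting; slurred speech; and one-sided weakness. These six fall in 3 of the AE form's 10 named groups.

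**Step 5. Effect on the primary analysis.** Section 7.1 defines the analysis population by at least one dose, and 7.3 does not list stopping the product as a reason for censoring. Leaving the study is one: 2.2.3 lets a participant with an adverse event exit, 4.2 withdraws anyone given a prescription, and 7.3 censors withdrawals. Any effect on the Kaplan-Meier estimate therefore comes through exits and withdrawals, not through stopping as such.

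**The case against.** The strongest reply is that the plan already makes the commitment twice, names the people who review adverse events, and nowhere says the advice must be printed. Staff can give it, and an AE form filed after a dose can reach them before the next packet. The consent form, the portal FAQs and the welcome-package information sheet are not available, nor are some pages after the AE form. Any of these could hold a stop rule. The study is classed as minimal risk, the ingredients are described as generally recognised as safe, the listed side effects are attributed to higher doses, and people with ingredient allergies are screened out. Many participants would stop on their own.

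Much of this stands. It rules out the inference that participants are never told to stop, and it is why the packet count starts at 0 and rests on an assumed delay. It does not remove the gap on the forms themselves. Advice read at consent may precede the cold by about 90 days or more, since the 90-day window starts only when product receipt is recorded. Staff contact has no stated time limit. The sponsor also chose both to promise the advice and to list these reactions.

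Two further inferences are not supported. A reader might want worsening symptoms, a stop trigger only in 2.2.3, carried into 6.4. Colds commonly worsen early, so that is a debatable trade-off and not a correction the documents require. A reader might also see a contradiction in 2.2.3 allowing participants to seek care while 6.4 advises it; that is a difference of wording.

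**Conclusion.** The point holds as a gap in delivery at the point of dosing. The protocol promises stop advice after an adverse event, the three available forms do not print it, and the written order of steps leads to another packet. The consequence for one participant is 0 or more extra packets, and 0 to 6 if contact is assumed to come within 3 days. The number of participants affected cannot be estimated from the documents.

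A reader might go further and infer that the primary analysis is biased. The documents do not support that, since stopping the product does not censor anyone.

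The conclusion rests on the available forms being the ones used when dosing. If the information sheet or portal carries the same line, the gap is smaller, but the diary and AE form would still lack it. The change should be made because it is cheap and specific to safety. Confidence is medium because of the unseen material.

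**What to change.** 1. Print *If you have a side effect, stop taking the product and contact the study team* in the Instructions for Use, at diary item 12 and at the top of the AE form. Add the same step to the side-effect bullet in 6.1.
2. On the AE form, add a *seek immediate medical care* prompt for the six reactions listed in Step 4 of the working.
3. State in 6.4 that stopping the product is not withdrawal, and that the diary continues to symptom resolution or day 18.

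Leave worsening symptoms out of 6.4.

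The cost is a minor amendment: wording in two protocol sections and on three forms. A few more participants may stop the product, exit, or see a doctor and be prescribed medication. Those who exit or are withdrawn are censored under 7.3, so some follow-up may be lost. Limiting the urgent prompt to the listed reactions and separating stopping from withdrawal should keep that loss small, though the documents give no basis for a number.

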4.2. Required Behavior

If the participant is prescribed antibiotics or any other medications for any reason, they should report this prescription and they will be withdrawn from the trial as of the prescription date.

Participants are asked not to ingest or take any other form of cold remedy (over-the-counter (NyQuil/Dayquil/Cough Syrup/Cough Drops/EmergenC/Airborne/Zarbee's or any similar cold-relief product or prescription drugs) during the 18-day study period. If taken during the study duration the participant will record this as part of their diary and will be exited from the study.

Because none of the active ingredients are aimed at pain relief or reducing fever, participants will be allowed to take pain relievers/fever reducers (Advil/Tylenol or their equivalent).

Participants are asked to limit the consumption of alcohol beverages to less than or equal to two drinks per day and avoid recreational drugs or use of cannabis during the study period.

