- At time of enrollment, participant will be given access to the HIPAA compliant study portal.
 - The study portal provides access to study information, signed informed consent form, instructions for product use, frequently asked questions, study surveys, symptom diary, and data collection tools.
- Participant shall complete baseline assessments upon access to the portal.
 - Baseline assessment will include questions regarding the participants' demographics, medications, detailed information regarding previous colds, including treatment.
- To ensure that baseline assessments are completed before test product is used by the
 participant, study materials and study welcome package will be shipped to the participant once
 the clinical study manager/clinical operations coordinator confirms that the baseline assessment
 has been completed.
- The welcome package will include an information sheet that will outline instructions for their participation in the trial, the test product, disposable thermometer, and paper forms of the

- documents (paper form of study documents will be provided for real time data collection, in the event that the participant cannot log into the study portal to input data).
- Once the participant receives the test product, the participant will log into the study portal to acknowledge the receipt of the test product.
- Study start date will be the date of acknowledgement of receipt of test product.
- Participant will be sent weekly email reminders that remind them of their participation in the study. Once the participant indicates they are experiencing a cold. The participant will be reminded by email daily to complete their symptom diary.
- At the onset of their cold symptoms, the participant will complete the cold start form.
 - Onset is defined as the point in time the participant experiences 2 or more cold symptoms (cough, hoarseness, muscle ache, nasal drainage, scratchy throat, sore throat, sneezing, oral temperature greater than 37.7°C (99.9 °F)).
 - If fever is a symptom that the participant experiences, they will use the provided disposable thermometer to take their temperature and record it in the diary.
- If the participant meets all the criteria for a cold, they will start their symptom diary prior to taking the test product.
- After completing the surveys, the participant will take the test product. The participant will mix 1 drink-mix packet into 6-8 oz of water and consume the whole drink.

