7.3. Analysis Plan

Time-dependent variable analysis

The primary analysis involves time dependent variables. The Kaplan-Meier algorithm will be used to analyze time to freedom from cold symptoms. Data presentation will include tables and graphs; in particular tables of participants at risk at various time points.

Censoring:

- Participants who do not have a cold during the trial will not be in the ITT population, and will
 not be included in the endpoint analysis.
- Participants who report the onset of a cold, but who do not complete the daily reports through
 18 days will be censored as of the date of the last report.
- Participants who still have cold symptoms at 18 days will be censored at that time.
- Participants will also be censored if they withdraw from the trial.

Secondary Endpoints:

- Analysis of the individual cold symptoms will be a presentation of median time until the
 individual symptom resolves. The median for this purpose is the value computed as part of
 the Kaplan-Meier algorithm.
- An additional analysis will investigate the relation between baseline age and gender, and the time to resolution.
- Adverse events will be summarized.
- An additional data presentation will consist of side by side presentation of results from both

Treatment and Control in similar studies appearing in the literature. There will be no formal statistical comparison of results from this study and historical studies.

General statistical methods:

Data will be analyzed using standard statistical methods, as further specified in a statistical analysis plan (SAP), which will be prepared in detail at a later date. [23]

- Data analysis will largely consist of summary statistics and graphs. The only formal statistical comparisons will be in covariate analyses.
- For continuous variables data presentation will consist of means, confidence intervals computed using the *t*-statistic, medians, and interquartile ranges. Group comparisons will use *t*-tests or ANOVA.
- For discrete variables confidence intervals will use the exact intervals, where available. Group comparisons will use Fisher's exact test, with the Monte Carlo version used where computationally necessary.
- For time to event variables analysis will use the Kaplan-Meier algorithm, and group comparisons will use the log-rank or proportional hazards methods, depending on the data type.
- Covariate analyses will investigate the relation between baseline and outcome variables, using

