There is one Serious Drug Interaction known for Zinc—do not take with Cephalexin, as it reduces the amount of the Cephalexin drug metabolized. There are also some theoretical Moderate Interactions, where Zinc may interact in the metabolism of certain drugs, or have other effects that could interfere with their effect. See Below for List.

AMILORIDE (Midamor)

Interaction Rating = **Minor** Be watchful with this combination. Severity = Insignificant • Occurrence = Probable • Level of Evidence = **B**

Amiloride can reduce urinary zinc excretion, especially at doses of 10 mg/day or more. This zinc-sparing effect can help to counteract zinc losses caused by thiazide diuretics, but it is unlikely to cause zinc toxicity at usual amiloride doses (830,11626,11627,11634). The other potassium-sparing diuretics, spironolactone (Aldactone) and triamterene (Dyrenium), do not seem to have a zinc-sparing effect.

ANTIDIABETES DRUGS

Interaction Rating = **Moderate** Be cautious with this combination. Severity = Moderate • Occurrence = Possible • Level of Evidence = **B**

Clinical evidence suggests that zinc can lower blood glucose levels (86933,87520,90201). Theoretically, zinc can have additive effects in patients treated with antidiabetic agents; use with caution. Dose adjustments to diabetes medications might be necessary. Some antidiabetes drugs include glimepiride (Amaryl), glyburide (DiaBeta, Glynase PresTab, Micronase), insulin, metformin (Glucophage), pioglitazone (Actos), rosiglitazone (Avandia), and others.

ATAZANAVIR (Reyataz)

Interaction Rating = **Moderate** Be cautious with this combination. Severity = Mild • Occurrence = Probable • Level of Evidence = **B**

There is some concern that zinc might decrease serum atazanavir levels by chelating with atazanavir in the gut and preventing its absorption (93578). Although a single dose of zinc sulfate (Solvazinc tablets) 125 mg orally does not affect atazanavir concentrations in patients being treated with atazanavir / ritonavir, co-administration of zinc sulfate 125 mg daily for 2 weeks reduces plasma levels of atazanavir by about 22% in these patients. However, despite this decrease, atazanavir levels still remain at concentration that is high enough to be effective for

preventing HIV virus replication (90216). Therefore, the 22% decrease in atazanavir levels is probably not clinically significant.

CEPHALEXIN (Keflex)

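### Section 4.2 withdraws anyone prescribed any medicine for any reason, but no form shown prompts for a prescription unrelated to the cold while the product is being taken

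*Combined protocol and SAP*

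**What the plan says.** Section 4.2 (Required Behavior) sets a broad rule: "If the participant is prescribed antibiotics or any other medications for any reason, they should report this prescription and they will be withdrawn". The withdrawal takes effect on the day the medicine was prescribed. Section 7.3 (Censoring) gives the consequence for the primary Kaplan-Meier analysis: "Participants will also be censored if they withdraw from the trial".

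Data come only from the participant, through the portal (Section 4.4). Section 6.1 says of the period after a cold is reported: "The participant will be reminded by email daily to complete their symptom diary". The diary (Appendix E) is thus the routine daily contact. Its items on medicines and care are:

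- Item 9: use of ibuprofen or acetaminophen.
- Item 10: "Have you taken any other cold medications (Nyquil, Dayquil, other cold medication, cough drop, cough syrup, etc".), with a yes leading to exit.
- Item 11: "Have you seen a doctor for your symptoms"? Only a yes opens item 11a, which asks whether anything was prescribed and directs exit if so.
- Item 12: "Did you experience any side effects after taking the product"? A yes leads to the Adverse Event form.

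The schedule in Section 6.2 ticks "Meds & Supplements" only before receipt of the product. The exit form (Appendix F) has no question on medicines.

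**The concern.** The rule covers every prescription, while the only prescription question on the diary covers those given at a visit for the cold. A participant who is prescribed something for another reason during the cold has to report it unprompted.

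Two things follow if the prescription goes unreported. First, the participant may keep taking 15 mg of zinc twice a day alongside a medicine that the sponsor's own Appendix A warns about. For one antibiotic the advice is "do not take with Cephalexin, as it reduces the amount of the Cephalexin drug metabolized", rated Major; quinolones and tetracyclines are rated Moderate. Appendix A gives timing advice that avoids or limits these interactions, but the Instructions for Use (Appendix B) give no spacing from other medicines. A missed report is therefore also a missed chance to pass on that advice. Second, someone whom 4.2 would withdraw and 7.3 would censor stays at risk in the primary curve.

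**Working it through.** **Do the forms cover the rule?** Take a participant on day 3 of a cold who is given an antibiotic by a dentist for a tooth infection.

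- Item 9: no, if no pain or fever reducer was taken.
- Item 10: no, because the antibiotic is not a cold medication.
- Item 11: no, because the visit was not for the cold. Item 11a is never reached.
- Item 12: no, if there was no side effect.

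Every answer is truthful, and the prescription is not recorded. There is one partial route. If item 12 is yes, Adverse Event form items 5 and 5a (Appendix G) ask about a doctor or hospital visit for that side effect and what treatment was given. A prescription for a perceived side effect could surface there, though it is not asked for as such and no exit follows. The cold start form is not shown. It is completed at onset, so it could not capture a later prescription.

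**How many people?** The documents give no prescription rate, so a range is assumed.

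Inputs:
- 80 treated participants, the plan's target: 200 × 0.40 = 80 (Section 7.2).
- p, the proportion receiving a prescription in 90 days at a constant rate: 10%, 20% or 30% (assumed).
- Length of cold: 7 days (assumed).

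Chance of a prescription during the cold = 1 − (1 − p)^(7/90):
- p = 10%: 0.0082, × 80 = 0.65 people
- p = 20%: 0.0172, × 80 = 1.38 people
- p = 30%: 0.0274, × 80 = 2.19 people

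Given the assumed rates, these are upper bounds. They include prescriptions that item 11 catches, that participants report unprompted, or that do not interact with the product.

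**How far could the primary curve move?** The extreme case is that all k affected people share one outcome state when half have recovered, and that under 4.2 all would have been censored at the start. The estimate then changes from 40/80 to 40/(80 − k), or by the same amount in the other direction. The shift is 0.5k/(80 − k):
- k = 0.65: 0.41 points
- k = 1.38: 0.88 points
- k = 2.19: 1.41 points

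The standard error at 50% with 80 people is √(0.25/80) = 0.0559, or 5.6 points. Even the extreme shift is at most about a quarter of that (1.41/5.59 = 0.25).

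**What does Appendix A support on the interaction?** Its measured effects come from large zinc sulfate doses. With 250 mg taken together with cephalexin, the antibiotic's peak fell 31% and exposure 27%. With 200 mg, tetracycline absorption fell 30% to 40%. No cephalexin effect was seen when zinc followed the antibiotic by 3 hours. Quinolones and tetracyclines are to be taken at least 2 hours before or 4 to 6 hours after zinc. Doxycycline is reported not to interact significantly. Nothing is given for 15 mg of zinc as gluconate.

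**The case against.** The strongest reply is that nothing is contradicted. Section 4.2 states the duty to report, and a form that does not repeat it leaves the rule intact. Section 11 already discloses reliance on self-report with no independent compliance check, and a new diary item would still be self-report. This stands: the point is about making a rule workable and does not show the rule to be wrong. A daily prompt still makes reporting likelier, and the plan already gives one for cold medicines, which also trigger exit.

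Three stronger readings are tempting, and the documents support none of them.

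- *Reporting rests on the participant's memory of 4.2 alone.* The welcome package has an information sheet, and the portal holds the signed consent and frequently asked questions (Section 6.1). None of these is shown, and any could repeat the duty. The claim must stay at the forms that are shown.
- *Participants face an established safety hazard.* Section 4.2 does not tie its rule to interactions. Harm would need an unreported prescription for an interacting medicine, taken at overlapping times, with a meaningful effect at a dose Appendix A does not address. Nor can the spacing advice be turned into a fixed block of the day that is closed to antibiotics, because Section 6.1 lets the two packets be more than 4 to 6 hours apart.
- *The primary result is biased.* The shift is small under extreme assumptions and has no known direction.

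**Conclusion.** The mismatch is real and minor. The withdrawal rule covers all prescriptions, and no form shown prompts for one unrelated to the cold during treatment, apart from the indirect Adverse Event route for a suspected side effect. On the assumed rates and a 7-day cold, at most about 0.7 to 2.2 of 80 participants are involved, and the effect on the primary curve is negligible. The main reason to act is that a prompt lets the study team stop the product, as 4.2 intends, when the new medicine is one Appendix A warns about. The risk at 15 mg of zinc is unknown. The counts depend on the assumed prescription rates; the comparison of rule and forms does not. This is a low-priority, cheap improvement.

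**What to change.** Keep diary item 11 and add one daily item that does not depend on a doctor visit: *Since your last entry, have you been prescribed any medicine, for any reason? (name, date)*. A yes leads to stopping the product, exit, and censoring at that date, which is what 4.2 and 7.3 already require. Ask the same once at cold start, covering the time since baseline, if that form does not already do so.

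The cost is one more diary question and possibly a few more censored participants. Sample size and analysis method are unchanged. If the sponsor thinks it too broad to exit people for unrelated prescriptions, it could instead narrow 4.2 to named classes of medicine. The diary item would still be needed, with the exit rule applied to those classes.
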